#### **8.5.1.1. Criteria for the Calculation of Apparent Terminal Elimination Rate Constant and Half-life**

The start of the terminal elimination phase for each subject will be defined by visual inspection and generally will be the first point at which there is no systematic deviation from the log-linear decline in concentrations.

The apparent terminal elimination rate constant ( $\lambda_z$ ) will only be calculated when a reliable estimate can be obtained using at least 3 data points, preferably not including  $C_{\max}$ , and the adjusted coefficient for determination of exponential fit ( $R^2$ -adj) of the regression line is  $\geq 0.7$ . Parameters requiring  $\lambda_z$  for their calculation (eg, AUC0-∞,  $t_{1/2}$ , CL/F, and Vz/F) will only be calculated if the  $R^2$ -adj value of the regression line is  $\geq 0.7$ .

The following regression-related diagnostic PK parameters will be determined, when possible:

Parameter	Units	Definition
$\lambda_z$	1/h	apparent terminal elimination rate constant
$\lambda_z$ Upper	h	end of exponential fit
$\lambda_z$ Lower	h	start of exponential fit
$\lambda_z$ N	NA	number of data points included in the log-linear regression
$\lambda_z$ Span Ratio	NA	time period over which $\lambda_z$ was determined as a ratio of $t_{1/2}$
$R^2$ -adj	NA	adjusted coefficient for determination of exponential fit

Where possible, the span of time used in the determination of  $\lambda_z$  (ie, the difference between  $\lambda_z$  Upper and  $\lambda_z$  Lower) should be  $\geq 2$  half-lives. If the  $\lambda_z$  Span Ratio is  $< 2$  half-lives, the robustness of the  $t_{1/2}$  values will be discussed in the CSR.

### **8.5.1.2. Criteria for Calculation and Reporting of Area Under the Concentration-time Curve**

The minimum requirement for the calculation of AUC will be the inclusion of at least 3 consecutive concentrations above the lower limit of quantification. If there are only 3 consecutive concentrations, at least 1 should follow  $C_{\max}$ .

If the extrapolated area is  $>30\%$ ,  $AUC_{0-\infty}$  (and derived parameters) may be excluded from the summary statistics and statistical analysis at the discretion of the sponsor or pharmacokineticist.

If  $AUC_{0-\infty}$  cannot be determined reliably for all subjects and/or dose levels, an alternative AUC measure, such as AUC to a fixed timepoint or  $AUC_{0-t_{last}}$ , may be used in the statistical analysis of dose proportionality.

### **8.5.1.3. Calculation of NST-6179 Urinary Parameters**

The amount of the dose administered recovered (Ae) in urine as NST-6179 for each urine collection interval ( $t_1-t_2$ ) will be calculated as the product of urine analyte concentration and urine volume. Where only urine sample weight is supplied, a specific gravity of 1 g/mL will be assumed, and it will be considered equivalent to urine volume.

Cumulative  $Ae_{0-x\text{ h}}$  will be calculated by summing the  $Ae_{t_1-t_2}$  values over the 0-x h interval, where x = the end of the last collection time interval.

The percentage of the dose administered recovered over the time interval  $t_1$  to  $t_2$  ( $fe_{t_1-t_2}$ ) as NST-6179 will be calculated for each urine collection interval as follows:

$$fe_{t_1-t_2} = (Ae_{t_1-t_2} / \text{dose}) \times 100$$

Cumulative  $fe_{0-x\text{ h}}$  will be calculated by summing the  $fe_{t_1-t_2}$  values over the 0-x h period in the same manner as cumulative  $Ae_{0-x\text{ h}}$ .

Renal clearance ( $CL_R$ ) will be calculated over 0- $t_2$  according to the following formula, where cumulative Ae and AUC are calculable to the same end time ( $t_2$ ):

$$CL_R = Ae_{0-t_2} / AUC_{0-t_2}$$

Alternatively,  $AUC_{0-\infty}$  may be used if urinary excretion of the dose is considered to be complete and  $AUC_{0-\infty}$  is well characterised.

### **8.5.1.4. Criteria for Handling Concentration Below the Limit of Quantification or Missing Concentrations for Pharmacokinetic Analysis**

Plasma concentrations below the limit of quantification (BLQ) will be assigned a value of 0 before the first measurable concentration and thereafter BLQ concentrations will be treated as missing. The following rules apply to the specific situations defined below:

- If an entire concentration-time profile is BLQ, it will be excluded from PK analysis.

- Where 2 or more consecutive concentrations are BLQ at the end of a profile, the profile will be deemed to have terminated and any further quantifiable concentrations will be set to missing for the calculation of the PK parameters, unless they are considered to be a true characteristic of the profile of the drug.
- If a Day 1 predose plasma concentration is missing, it will be set to 0 by default within Phoenix WinNonlin. If a profile day 14 predose concentration is missing, it will be set to Cmin by default within Phoenix WinNonlin.

Urine concentrations that are BLQ will be set to 0 for the calculation of  $Ae_{t1-t2}$ .

#### **8.5.1.5. Treatment of Outliers in Pharmacokinetic Analysis**

If a value is considered to be anomalous due to being inconsistent with the expected PK profile, it may be appropriate to exclude the value from the PK analysis. However, the exclusion of any data must have strong justification and will be documented in the CSR.

Any quantifiable predose concentration value on Day 1 will be considered anomalous and set to missing for the PK analysis. This will be set to 0 by default in Phoenix WinNonlin.

#### **8.5.2. Presentation of Pharmacokinetic Data**

All PK concentrations and parameters will be listed.

Summary tables, arithmetic mean (+ standard deviation [SD]) figures, overlaying individual figures, and individual figures by treatment and time postdose will be provided for plasma PK concentrations. All figures will be produced on both linear-linear and linear-logarithmic scales, with the exception of figures across all days, which will be produced on the linear-linear scale only. The +SD bars will only be displayed on the linear-linear scale.

Summary tables by treatment will be provided for all PK parameters, with the exception of diagnostic regression-related PK parameters. Separate summary tables by treatment and time interval will be provided for excretion parameters and cumulative excretion parameters.

A subject may be excluded from the PK summary statistics and statistical analysis if the subject has an AE of vomiting that occurs at or before 2 times the median  $t_{max}$ .

If the actual time of sample collection deviates from the nominal time by more than  $\pm 10\%$ , the plasma concentration will be flagged in the listings. Individual concentrations deemed to be anomalous will be flagged in the listings.

For plasma concentration data the following rules will apply:

- Values that are BLQ will be set to 0 for the calculation of summary statistics.
- Arithmetic mean or median values that are BLQ will be presented as 0.

Urine concentration data will be listed only.

For PK parameters the following rule will apply:

- Geometric mean and coefficient of variation will not be calculated for discrete time parameters (ie,  $t_{max}$  or  $t_{last}$ ).

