t _{max} ^b (h)	1.25 (1.00-3.00)	1.25 (1.00-2.00)	2.00 (1.00-3.00)	1.50 (1.00-3.00)	2.00 (1.00-4.00)	2.00 (1.00-2.00)
t _{1/2} (h)	1.04 (37.2)	1.01 (16.6)	1.19 (31.5)	1.64 (113.0)	2.33 (56.5)	3.22 (20.0)
C _{min} (ng/mL)	NA	NC	NC	NC	NA	8.10 (28.9)
RA _{AUC0-τ}	NA	1.14 (15.5)	NA	1.13 (18.7)	NA	1.21 (17.6)
RA _{Cmax}	NA	1.22 (32.3)	NA	0.953 (46.7)	NA	1.09 (39.9)

Note: C_{min} values are NC because the minimum concentration in all profiles was 0, and geometric mean was not calculated.

^a Refers to a AUC₀₋₂₄ for Day 1.

^b Median (min-max) presented.

N = number of subjects; NA = not applicable; NC = not calculated; QD = once daily; RA = accumulation ratio.

To date, none of the subjects receiving single or repeat administration of NST-6179 have exceeded the PK stopping criteria. Following single administration of 1000 mg NST-6179 (Cohort A5), the highest individual systemic NST-6179 exposure represented 73.8% and 25.2% of the stopping criteria for C_{max} and AUC₀₋₂₄, respectively. Following repeat

administration of 1000 mg NST-6179 QD for 14 days (Cohort B3), the highest individual systemic NST-6179 exposure represented 88.2% and 34.1% of the PK stopping criteria, based on C_{max} and AUC_{0-24} , respectively.

Overall, PK across the dose range of 50 to 1000 mg was generally consistent, with median t_{max} between 1 to 2 hours postdose, estimates for $t_{1/2}$ in the range of 1 to 3 hours, and no evidence of accumulation following QD administration. From 50 to 1000 mg, AUC and C_{max} increased in a manner that was generally proportional (or slightly more than proportional) to the increase in dose; as dose increased by 20-fold, geometric mean C_{max} and $AUC_{0-\infty}$ increased by 24- to 26-fold, respectively.

1.6.1.2. *Clinical Safety*

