**Part B - MAD**

Parameter	Units a	Definition
Plasma PK Parameters		
AUC 0-<math>\tau</math>	h*ng/mL	area under the concentration-time curve over a dosing interval, may be referred to AUC 0-24 for Day 1 b
AUC 0-<math>\infty</math>	h*ng/mL	area under the concentration-time curve from time 0 extrapolated to infinity c (Day 1 only)
%AUC extrap	%	percentage of area under the concentration-time curve due to extrapolation from the last quantifiable concentration to infinity (Day 1 only)
C max	ng/mL	maximum observed concentration
C min	ng/mL	minimum observed concentration in a dosing interval (Day 14 only)
t max	h	time of the maximum observed concentration
t last	h	time of the last quantifiable concentration
t 1/2	h	apparent terminal elimination half-life
CL/F	L/h	apparent total clearance
V z/F	L	apparent volume of distribution during the terminal phase
RA AUC0-<math>\tau</math>	NA	observed accumulation ratio based on AUC 0-<math>\tau</math>
RA Cmax	NA	observed accumulation ratio based on C max
DAUC 0-<math>\tau</math>	h*ng/mL/mg	AUC 0-<math>\tau</math> normalised by dose administered d
DAUC 0-<math>\infty</math>	h*ng/mL/mg	AUC 0-<math>\infty</math> normalised by dose administered d (Day 1 only)
DC max	ng/mL/mg	C max normalised by dose administered d
Urine PK Parameters		
Ae t1-t2	mg	amount of the dose administered recovered over the time interval t 1 to t 2 , calculated for each interval from the start of the collection interval and from the start of the dosing interval (time 0)
fe t1-t2	%	percentage of the dose administered recovered over the time interval t 1 to t 2 , calculated for each interval from the start of the collection interval and from the start of the dosing interval (time 0)
CL R	L/h	renal clearance, calculated as Ae/AUC using matched collection intervals; at steady state, collection intervals will be matched to the dosing interval

a Units are based on concentration units (provided by the bioanalytical lab or preferred units for presentation of PK parameters) and dose units used in the study.

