b The AUC will be calculated using the linear trapezoidal rule for increasing concentrations and the logarithmic rule for decreasing concentrations (linear up/log down rule).

c Based on the last observed quantifiable concentration

d Calculated by dividing the parameter by the dose (mg)

Additional PK parameters may be determined where appropriate.

The PK analysis will be carried out where possible using actual dose administered (mg) and actual postdose blood sampling times. If an actual time is missing, the sample concentration result will be treated as missing unless there is scientific justification to include the result using the nominal time.

The parameters  $C_{\max}$ ,  $C_{\min}$ , and  $t_{\max}$  will be obtained directly from the concentration-time profiles. If  $C_{\max}$  occurs at more than 1 timepoint,  $t_{\max}$  will be assigned to the first occurrence of  $C_{\max}$ .

The accumulation ratio(s) (RAAUC0-τ and RACmax) will be calculated as follows:

$$RA_{AUC_{0-\tau}} = AUC_{0-\tau} \text{ profile day 14} / AUC_{0-\tau} \text{ profile day 1}$$

$$RA_{C_{\max}} = C_{\max} \text{ profile day 14} / C_{\max} \text{ profile day 1}$$

The parameter AUC0-tlast or other common partial area may be used to determine RAAUC0-τ if AUC0-τ cannot be reliably calculated for the majority of subjects.

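### The SAP's BLQ rule makes Day 14 Cmin depend on which trough sample is below the limit, and nothing says how a Cmin of 0 enters the summary

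*SAP*

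**What the plan says.** SAP 3.2 lists Cmin among the Part B secondary endpoints. The Part B parameter table in SAP 8.5.1 restricts it to Day 14 and defines it over a dosing interval. The text below that table says that Cmax, Cmin and tmax "will be obtained directly from the concentration-time profiles".

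SAP 8.5.1.4 gives the BLQ rule for PK analysis: a BLQ plasma concentration is "assigned a value of 0 before the first measurable concentration and thereafter BLQ concentrations will be treated as missing". It adds: "If a profile day 14 predose concentration is missing, it will be set to Cmin by default within Phoenix WinNonlin".

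SAP 8.5.2 provides summary tables for all PK parameters except the regression diagnostics. Its only restriction on the statistics is "Geometric mean and coefficient of variation will not be calculated for discrete time parameters", with tmax and tlast named. The instruction in the same section to count BLQ as 0 stands under plasma concentration data, not under PK parameters.

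The note to Protocol Table 7 (section 1.6.1.1) explains the Cmin entries marked NC: "the minimum concentration in all profiles was 0, and geometric mean was not calculated".

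**The concern.** Setting late BLQ values to missing is a rule made for AUC and the terminal slope. Applied to a minimum, it can remove the very observation that defines the parameter. Under once-daily dosing the Day 14 trough is sampled twice, at predose and at 24 h, and the rule treats the two samples differently. Two subjects with equally low troughs can therefore receive quite different Cmin values.

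The second gap is in the summary. Half-life is about 1 to 3 h and dosing is once daily, so BLQ troughs are to be expected, and Table 7 shows that they occurred. A geometric mean and CV are not defined on data containing zeros, yet the SAP does not exempt Cmin from them. Protocol 3.4 says Part B aims to reach and hold steady-state levels, so the share of subjects with no measurable trough is worth reporting plainly.

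**Working it through.** **Inputs.** The BLQ and missing-predose rules are from SAP 8.5.1.4, and the Cmin definition is from SAP 8.5.1. Day 14 QD sampling within the interval is from Protocol Appendix 6: predose, 0.5, 1, 1.5, 2, 3, 4, 6, 8, 12 and 24 h, with nothing between 12 and 24 h. That schedule is in protocol Version 5. The Version 4 to 5 change list describes added BID sampling and records no change to the QD times. Interim values are from Protocol Table 7. The limit of quantification, L, is not given.

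**1. Table 7 first.** The NC entries at 200 and 400 mg QD agree with the rule: a BLQ predose sample gives Cmin = 0, and ln(0) is undefined. The 1000 mg entry, 8.10 (28.9) ng/mL under a column headed N=8, cannot be reproduced without individual values. As a check that the table is read correctly, ratios of its Day 14 to Day 1 geometric means return the stated accumulation ratios to within 0.01. Examples are 12900/11300 = 1.142 (stated 1.14) and 85700/71100 = 1.205 (stated 1.21).

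**2. The rule applied to Day 14.**

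| Predose | 24 h | Effect of 8.5.1.4 | Cmin |
|---|---|---|---|
| BLQ | any | predose set to 0 | 0 |
| quantifiable | BLQ | 24 h set to missing | lowest remaining value, at least L |
| missing | BLQ | 24 h set to missing; predose filled with Cmin | lowest quantifiable value from 0.5 to 12 h |

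In rows 2 and 3 a concentration below L was observed, so the true minimum is below L while the reported one is at or above it. The error is always upward. In row 3 the too-high value is then also used as the predose value.

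The table assumes that the rule is applied profile by profile and that the 0.5 h sample is quantifiable. If the rule were instead applied to a subject's whole record, a BLQ Day 14 predose sample would also be missing. The zeros in Table 7 point to the profile-by-profile reading.

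**3. The summary.** Geometric mean = exp(mean of ln Cmin). One zero in a group leaves it, and the geometric CV, undefined. The SAP gives no convention for this case.

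**4. What 8.10 could stand for (conditional).** Taking the CV as geometric and the values as log-normal:
- log SD = sqrt(ln(1 + 0.289²)) = 0.283
- arithmetic mean = 8.10 × exp(0.283²/2) = 8.43

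If k of the 8 subjects had Cmin = 0 and 8.10 came from the others, the arithmetic mean over all 8 would be 8.43 × (8 − k)/8. That is 8.43, 7.38, 6.32 and 5.27 ng/mL for k = 0, 1, 2 and 3. The value of k is not stated and may be 0.

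**5. Can row 3 be sized?** One could extrapolate from Table 7 with a mono-exponential decline from Cmax at median tmax. At 1000 mg this gives 31800 × 2^(−(24 − 2.00)/3.22) = 279 ng/mL at 24 h, against a stated Cmin of 8.10, which is about 34 times too high. The shape fails its only check, so no size is derived from it.

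**The case against.** The case for leaving this alone is substantial.

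- The usual pattern is a BLQ predose sample, and there the rule gives 0 consistently, as it did in every 200 and 400 mg profile. Rows 2 and 3 need a 24 h BLQ sample with a quantifiable or missing predose sample. Subjects are resident on Day 14, and the documents do not show that either pattern occurred.
- All parameters and concentrations are listed individually. Plasma concentrations are summarised by time with BLQ as 0, so the predose and 24 h troughs appear under one consistent rule.
- Cmin enters neither the dose-proportionality model (SAP 8.5.3) nor the stopping criteria (Protocol 3.7). The plan's accumulation measures are ratios of AUC and Cmax, so nothing here bears on a conclusion about accumulation.
- The TFL shells, which are not among the documents, may already state a convention and a per-parameter count.

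This limits the consequence, but it does not supply the rule. The Table 7 note covers only the all-zero case, and it stands in a protocol version that SAP section 1 says was never used for study conduct.

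A reader might go further and infer that zeros are silently dropped from the geometric mean. The documents do not say so. The SAP is silent, and the one documented instance was openly marked NC. A reader might also take 8.10 (28.9) at 1000 mg as coming from a quantifiable subset. The table neither shows nor excludes that.

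**Conclusion.** The point holds and is minor. As written, SAP 8.5.1.4 gives too high a Cmin when the 24 h sample is BLQ and the predose sample is quantifiable or missing. SAP 8.5.2 leaves undefined a summary that it does not exempt, for data known to contain zeros. That a geometric mean is intended for Cmin is inferred from the exclusion naming only tmax and tlast.

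The direction of the error follows from the rule alone, given the profile-by-profile reading. Its size cannot be derived, because the limit, the individual values and the number of zeros at 1000 mg are not given. Only a descriptive secondary endpoint in Part B is affected. The same gap exists in principle for interval urinary excretion, where BLQ urine is set to 0, but the documents contain no urine results, so zeros there are not documented.

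**What to change.** In SAP 8.5.1.4, add that for Cmin a BLQ value at any sample from the start to the end of the dosing interval (predose to 24 h for QD) counts as BLQ and is 0 in calculations, and that Cmin is not derived when both trough samples are missing. The existing rule can stay for AUC and the terminal slope.

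In SAP 8.5.2, for Cmin report n, number and percentage BLQ, median, minimum and maximum, and show geometric mean and CV as NC when any value in the group is 0. Apply the same NC convention to any interval Ae or fe that contains zeros.

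The cost is a few sentences and one extra row in the parameter table, with no new data. The downside is that a group with any BLQ trough has no geometric mean for Cmin.

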### 8.5.3. Pharmacokinetic Statistical Methodology

A statistical analysis will be conducted to investigate the dose proportionality of  $AUC_{0-t_{last}}$ ,  $AUC_{0-\infty}$ , and  $C_{max}$  on profile day 1 for Part A;  $AUC_{0-\infty}$  and  $C_{max}$  on profile day 1 and  $AUC_{0-\tau}$  and  $C_{max}$  on profile day 14 for Part B (only for plasma NST-6179).

The hypothesis testing will be 2-sided and carried out on 0.05 significance level.

The PK parameters will be analysed using a power model that will have the following form:

$$\text{parameter} = \text{intercept} \times \text{dose}^{\text{slope}} \times \text{random error}$$

Using the natural log (ln) transformation, a power model can be expressed as a linear regression equation:

$$\ln(\text{parameter}) = \text{intercept} + \text{slope} \times \ln(\text{dose}) + \text{random error}$$

For dose proportionality, the slope of the regression line is equal to 1; for dose independence, it is equal to 0.

For each PK parameter separately, a pooled estimate (across all doses) of slope, corresponding 95% confidence interval (CI), and between-subject CV will be calculated. Figures (on the logarithmic-logarithmic scale) containing individual values, power model line (95% CI), and dose proportionality line (defined as the power model line with slope of 1) will be created for each PK parameter. Additionally, figures (on the logarithmic-linear scale) containing individual values and geometric means will be created for each corresponding PK parameter normalised by dose administered.

The lack of fit test will be conducted for the statistical assessment of linearity assumption, and thus appropriateness of a power model. The lack of fit model will be the same as the power model fitted, but with dose included as additional fixed effect. The statistical assessment will rule the linearity assumption acceptable if the diagnostic plots appear reasonable and the lack of fit 2-sided p-value  $>0.05$  (dose effect is not significant at the 0.05 level of significance). The assessment of linearity assumption may also occur via visual examination of the figures by the pharmacokineticist. This assessment may override the statistical assessment; where this occurs, it will be detailed in the CSR.

It will be concluded that PK parameter is dose proportional for the dose range studied if the assumption of linearity is ruled acceptable and the 95% CI for the slope spans 1.

If the assumption of linearity is ruled unacceptable for any PK parameter, its corresponding PK parameter normalised by dose administered will be ln-transformed and analysed using an analysis of variance (ANOVA) model. The model will include dose as a factor.

For each PK parameter separately, the geometric least squares mean (GLSM) for each dose, p-values for the overall, and pairwise dose comparisons will be calculated. Residual plots will be produced to assess the adequacy of the model(s) fitted.

Examples of the SAS code that will be used are as follows:

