1.6. Summary of Clinical Experience

1.6.1. Phase 1 Single Ascending Dose and Multiple Ascending Dose Study in Healthy Subjects (Study NST-6179-01, ongoing)

The study remains blinded to treatment assignment for individual subjects. However, clinical PK and safety are available from the completed cohorts and are presented here to support the continued dose escalation in this ongoing study.

1.6.1.1. *Clinical Pharmacokinetics*

The PK data of NST-6179 were evaluated for all completed dosing cohorts and reviewed as part of the dose escalation meetings for both the single and repeated dose cohorts. Single doses of 50 mg, 200 mg, 400 mg, 600 mg, and 1000 mg were tested under fasted conditions. Repeat dosing performed under fasting conditions at the 200 mg, 400 mg, and 1000 mg dosing levels QD for 14 days. Standard PK parameters, accumulation ratio and dose proportionality were evaluated as appropriate. The PK parameters are presented for the completed single and repeated dose cohorts in [Table 6](#) and [Table 7](#), respectively.

Table 6: Geometric Mean (%CV) PK Parameters of NST-6179 Following Single Oral Administration of NST-6179 Under Fasting Conditions (Part A)

Parameter (Units)	NST-6179				
	50 mg	200 mg	400 mg	600 mg	1000 mg
Cohort	A1 N=6	A2 N=6	A3 N=6	A4 N=6	A5 N=6
AUC _{0-tlast} (ng*h/mL)	2490 (22.3)	10400 (29.0)	27200 (20.5)	39900 (23.0)	71400 (17.2)
AUC _{0-∞} (ng*h/mL)	2680 (16.4)	10500 (28.6)	27200 (20.5)	40000 (23.0)	71500 (17.2)
AUC ₀₋₂₄ (ng*h/mL)	2680 (16.4)	10500 (28.6)	27200 (20.5)	40000 (23.0)	71400 (17.2)
C _{max} (ng/mL)	1100 (54.7)	4880 (49.9)	13200 (29.2)	18300 (33.7)	26900 (33.7)
t _{max} ^a (h)	1.50 (1.00-4.00)	1.75 (1.00-4.00)	2.00 (1.50-3.00)	1.50 (0.500-2.00)	2.00 (1.00-3.00)
t _{1/2} (h)	0.844 (8.6)	1.05 (59.2)	1.38 (40.4)	1.71 (50.2)	2.91 (76.2)

^a Median (min-max) presented.

N = number of subjects.

Table 7: Geometric Mean (%CV) PK Parameters of NST-6179 Following Repeated Oral Administration of NST-6179 Under Fasting Conditions (Part B)

Parameter (Units)	NST-6179					
	200 mg QD		400 mg QD		1000 mg QD	
Cohort	B1		B2		B3	
	Day 1 N=8	Day 14 N=8	Day 1 N=8	Day 14 N=8	Day 1 N=8	Day 14 N=8
AUC _{0-τ} ^a (ng*h/mL)	11300 (41.5)	12900 (31.6)	21900 (36.6)	24700 (26.7)	71100 (16.0)	85700 (19.8)
AUC _{0-∞} (ng*h/mL)	11300 (41.4)	NA	21900 (36.6)	NA	71100 (16.0)	NA
C _{max} (ng/mL)	5690 (51.0)	6920 (28.0)	10500 (60.4)	10000 (34.9)	29100 (25.3)	31800 (39.9)

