## 5. SAMPLE SIZE JUSTIFICATION

No formal statistical assessment, in terms of sample size, has been conducted as this is the first time NST-6179 is being administered to humans. However, the number of subjects in each part of the present study is common in early clinical pharmacology studies and is considered sufficient to achieve the objectives of the study.

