# **8. STATISTICAL METHODOLOGY**

## **8.1. General**

Listings will be provided for all data captured in the database, with the exception of medical history. Listings will include all subjects assigned to the all subjects population and include data up to the point of study completion or discontinuation. Subjects are generally considered to have completed the study if they complete the scheduled follow-up visit (rather than early termination visit). Any subject who discontinues the study will be identified accordingly in the listings. Summaries will include the subjects assigned to the relevant population based on data type.

Data analysis will be performed using the SAS® statistical software package Version 9.4 (or higher if a new version is issued during the study).

Analysis Data Model (ADaM) datasets will be prepared using Clinical Data Interchange Standards Consortium (CDISC) ADaM Version 2.1 (or higher if a new version is issued during the study) and CDISC ADaM Implementation Guide Version 1.1 (or higher if a new version is issued during the study). Pinnacle 21 Community Validator Version 4.0.1 (or higher if a new version is issued during the study) will be utilised to ensure compliance with CDISC standards.

For all statistical analyses, the hypothesis testing will be 2-sided and carried out on 0.05 significance level, unless specifically stated otherwise.

Caution should be used when interpreting results from the statistical analyses conducted in this study because the sample size is not based on power calculations.

Where reference is made to 'valid' data, this refers to non-missing data which meet the predetermined criteria (eg, are not flagged for exclusion).

Where reference is made to 'all calculations', this includes, but is not limited to, summary statistics, statistical analyses, baseline derivation, and changes from baseline.

All figures will be produced on linear-linear or discrete-linear scales, as applicable, unless specifically stated otherwise.

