#### **8.6.6. Safety and Tolerability Statistical Methodology**

No inferential statistical analyses are planned.

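### SAP 8.5.3 turns failure to reject a slope of 1 into a conclusion of dose proportionality, with no acceptance range

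*SAP*

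**What the plan says.** SAP 8.5.3 fits a power model, a straight line of log parameter on log dose, with two-sided testing at the 0.05 level. Linearity is accepted if the lack-of-fit p-value exceeds 0.05 and the diagnostic plots look reasonable; the pharmacokineticist may override this by eye. The SAP then fixes the conclusion in advance, under which each parameter will be called "dose proportional for the dose range studied if the assumption of linearity is ruled acceptable and the 95% CI for the slope spans 1". It gives no wording for an interval that excludes 1. "If the assumption of linearity is ruled unacceptable for any PK parameter", the dose-normalised parameter goes to ANOVA instead.

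Protocol 8.3 names the power model but states no decision rule. Neither document gives an acceptance range for the slope or for a dose-normalised ratio. On sample size, SAP 5 says: "No formal statistical assessment, in terms of sample size, has been conducted". SAP 8.1 adds: "Caution should be used when interpreting results from the statistical analyses conducted in this study because the sample size is not based on power calculations".

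The SAP also requires the slope, its 95% CI, the between-subject CV and plots to be reported (8.5.3). SAP 8.5.2 says: "Summary tables by treatment will be provided for all PK parameters", apart from regression diagnostics, so the dose-normalised parameters are covered.

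**The concern.** A 95% CI that contains 1 shows only that the data do not contradict proportionality at that level. It does not show that the slope is close to 1. If the true slope is 1, the interval covers 1 about 95% of the time whatever the variance. If it is not 1, more variability or fewer subjects make the wrong declaration more likely. With no acceptance range and no precision calculation, nothing in the plan limits how imprecise a declared result may be.

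Dose proportionality is the only planned analysis with a hypothesis test; for safety, SAP 8.6.6 says "No inferential statistical analyses are planned". This one sentence fixes what is concluded from it. The sponsor's own reading of the interim data, in Protocol 1.6.1.1, is more careful: AUC and Cmax "increased in a manner that was generally proportional (or slightly more than proportional) to the increase in dose". Applied to the same figures, the SAP rule would drop that qualification for Cmax.

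**Working it through.** The documents contain no power or precision figure to reproduce, so I applied the SAP rule to the protocol's own interim data.

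**Inputs.** Geometric means and %CVs from Protocol Table 6 (A1 to A5: 50, 200, 400, 600, 1000 mg) and Table 7 (B1 to B3: 200, 400, 1000 mg once daily). Assumed: %CV is geometric, with 6 (Part A) or 8 (Part B) evaluable active subjects per dose.

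**Formulas.**
- Within-dose log variance = ln(1 + CV²).
- Slope = Sxy/Sxx, with x = ln(dose). Sxx = 32.325 in Part A (28 df) and 10.428 in Part B (22 df).
- Residual SS = pure error + lack of fit; SE = √(residual SS/df)/√Sxx.
- Exposure relative to proportional, top versus bottom dose = r^(slope−1), with r = 20 (Part A) or 5 (Part B).

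**Worked case, Part A Cmax.** Inputs: 1100 (54.7), 4880 (49.9), 13200 (29.2), 18300 (33.7), 26900 (33.7).
- Slope = 35.600/32.325 = 1.101.
- Residual SS = 3.905 + 0.312 = 4.217; SE = √(4.217/28)/√32.325 = 0.0683.
- 95% CI = 1.101 ± 2.048 × 0.0683 = 0.961 to 1.241.
- Relative exposure: 20^0.101 = 1.35; limits 20^(−0.039) = 0.89 and 20^0.241 = 2.06.
- Lack of fit p = 0.581.

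**All seven analyses.**

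| Analysis | Slope (95% CI) | Relative to proportional (95% CI) | Lack-of-fit p | Declared proportional? |
|---|---|---|---|---|
| A Cmax | 1.101 (0.961–1.241) | 1.35 (0.89–2.06) | 0.581 | Yes |
| A AUC0-∞ | 1.107 (1.031–1.184) | 1.38 (1.10–1.73) | 0.439 | No |
| A AUC0-tlast | 1.132 (1.052–1.211) | 1.48 (1.17–1.88) | 0.565 | No |
| B Day 1 AUC0-∞ | 1.150 (0.945–1.356) | 1.27 (0.91–1.77) | 0.360 | Yes |
| B Day 1 Cmax | 1.019 (0.736–1.302) | 1.03 (0.65–1.63) | 0.648 | Yes |
| B Day 14 AUC0-τ | 1.186 (1.015–1.357) | 1.35 (1.02–1.78) | 0.156 | No |
| B Day 14 Cmax | 0.964 (0.735–1.194) | 0.94 (0.65–1.37) | 0.061 | Yes, if linearity is accepted |

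**CV swap, geometric means unchanged.** Part A Cmax with the AUC0-∞ CVs gives 1.101 (1.019–1.183), lack-of-fit p 0.103: not declared. Part A AUC0-∞ with the Cmax CVs gives 1.107 (0.970–1.244), p 0.845: declared. For this pair the CVs alone decide the conclusion.

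**Chance that the CI spans 1 when the slope is not 1.** This uses the noncentral t with noncentrality (true slope − 1)√Sxx/s, where s is the pooled within-dose log-SD. The true slopes are illustrative.

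| Analysis (s) | True slope 1.10 | True slope 1.20 |
|---|---|---|
| A AUC0-∞ (0.213) | 27% | 0.1% |
| A Cmax (0.395) | 72% | 21% |
| B Day 14 AUC0-τ (0.260) | 78% | 34% |
| B Day 1 AUC0-∞ (0.321) | 84% | 51% |
| B Day 14 Cmax (0.336) | 85% | 55% |
| B Day 1 Cmax (0.449) | 89% | 72% |

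These figures cover the CI condition only; the linearity check passes about 95% of the time when the power model holds and lowers them slightly. The effect of study size is similar: with the five Part A doses, CV 40% and a true 1.5-fold excess over the range, the chance is 66% with 4 subjects per dose, 51% with 6, 21% with 12 and 2% with 24.

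**Sensitivity.** Taking log-SD = CV directly leaves every interval on the same side of 1 (Part A Cmax 0.955–1.248; Part A AUC0-∞ 1.030–1.184). With only 5, 4 or 3 evaluable subjects at 50 mg, the Part A AUC0-∞ interval still excludes 1 (lower limits 1.029, 1.026, 1.024).

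**The case against.** The SAP does not hide imprecision. It requires the slope, CI, CV, plots and dose-normalised summaries. Its caution in 8.1 must refer mainly to this analysis, since nothing else is tested. The rule also discriminates well for Part A AUC and withholds the label from three of the four AUC analyses. Of the declared results, Part B Day 1 and Day 14 Cmax have slopes of 1.019 and 0.964, so the label there overstates precision rather than hiding a visible departure. The slopes of 1.10 and 1.20 are illustrative; neither document says what departure matters. Any rule that splits on whether a CI contains 1 depends on variance, and the amended wording keeps that split.

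Most of this stands as a limit on size. The clear examples are Part A Cmax and Part B Day 1 AUC0-∞. The lack of a sample-size calculation is openly disclosed and is normal in a first-in-human study; it matters here only because an unpowered non-rejection cannot carry a positive claim. But the reported statistics and the caution only let a reader disagree with the conclusion. They do not change what the SAP says will be concluded.

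**Conclusion.** The concern holds and should be fixed. On the interim figures, three of seven analyses would be declared dose proportional, or four if linearity is accepted for Part B Day 14 Cmax. For Part A Cmax the declaration would stand beside an interval of 0.89 to 2.06 times proportional exposure, while AUC0-∞, with almost the same slope, would not be declared. The rule is weak mainly for Cmax and for Part B.

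This rests on rounded interim summaries for groups A1 to A5 and B1 to B3, geometric CVs and full evaluable numbers. Diagnostic plots and the visual override cannot be checked from summary data, and final results may differ. The fault lies in the rule itself and does not depend on these data. Its reach is limited: the analysis is secondary, the conclusion is confined to the doses studied, the primary safety objective is unaffected, and Protocol 3.6 and 3.7 base escalation on data review and predicted individual exposure.

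**What to change.** Replace the concluding sentence in SAP 8.5.3 with text to this effect:

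> Where linearity is accepted and the slope's 95% CI contains 1, the report will state only that no statistically significant departure from dose proportionality was detected. Where the CI excludes 1, the report will state that a departure was detected, and its direction. Interpretation in both cases will rest on the slope estimate and its CI.

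For every parameter, also report r^(slope−1), the model-based ratio of dose-normalised exposure at the highest versus the lowest dose, with its 95% CI. This only re-expresses the slope, but it shows parameters with similar slopes as similar. If the sponsor wants a positive conclusion, it must pre-specify and justify its own acceptance range.

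The cost is one sentence, one derived column and a new SAP version, since the current one is final. Protocol 8.3 need not change. Because group-level PK results are already known, the change should be justified on principle and not by which results it alters. On the interim figures, Part A Cmax, Part B Day 1 AUC0-∞, Part B Day 1 Cmax and possibly Part B Day 14 Cmax would receive a weaker statement than they do now. The ANOVA fallback also has no conclusion rule, and this change does not supply one.
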